8.3. Columbia Suicide Severity Rating Scales (C-SSRS)

The number and percentage of subjects with a response of “Yes” by categories for suicidal ideation, suicidal behavior and suicidal ideation or behavior will be summarized descriptively by visit. The listing for C-SSRS will be provided.

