### 3.3 Risk/Benefit Assessment

#### 3.3.1 Known Potential Risks

The safety of Qelbree has been evaluated in 189 adult participants (18 to 60 years of age) with ADHD exposed to one or more doses ranging from 200 mg to 600 mg QD in a short-term (6 week), randomized, double-blind, placebo-controlled trial (Study 812P306). Approximately 9% of the 189 participants receiving Qelbree discontinued treatment due to an adverse reaction. The adverse reactions most commonly associated with discontinuation of Qelbree were fatigue (n=4), insomnia (n=3), constipation (n=3), and headache (n=2). The most commonly reported adverse reactions (occurring at  $\geq 5\%$  and at least twice the placebo rate of Qelbree) were insomnia, headache, somnolence, fatigue, nausea, decreased appetite, dry mouth, and constipation ([Qelbree PI](#)).

Adverse Events of concern include ([Qelbree PI](#)):

- Suicidal Thoughts and Behavior: Among 189 adults treated with Qelbree, a total of three participants (1.6%) reported suicidal ideation on the C-SSRS, versus 0 of 183 adults treated with placebo. No adults treated with either Qelbree or placebo reported suicidal behavior on the C-SSRS in the study. No attempted or completed suicides occurred in the trial. Participants treated with Qelbree had higher rates of insomnia and irritability. Although a causal link between the emergence of insomnia and irritability and the emergence of suicidal impulses has not been established, there is a concern that these and other symptoms such as depressed mood, anxiety, agitation, akathisia, mania, hypomania, panic attacks, impulsive behavior, and aggression may represent precursors to emerging suicidal ideation or behavior.
- Blood Pressure and Heart Rate Increases: In a clinical study in adult participants (18 to 60 years of age), 52/178 (29%) of participants treated daily with Qelbree (200 mg to 600 mg) had a  $>20$  beat per minute (bpm) increase in pulse rate at any time point in the clinical trial, compared to 23/181 (13%) of participants who received placebo. Of participants treated daily with Qelbree (200 to 600 mg), 23/178 (13%) had a  $\geq 15$  mmHg increase in diastolic blood pressure at any time in the clinical trial, compared to 16/181 (9%) of participants in the placebo group.

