**Figure 1. Protocol Schema**

### 6.1 Screening Period

The duration of the screening period is up to 4 weeks (28 days) starting from the date of Screening televisit (e.g. Televisit #1a) after obtaining informed consent. The Screening Period includes two virtual televisits. The first televisit should occur within 3 weeks after the date of obtaining informed consent. If a potential participant is still considered eligible after Televisit 1a, the second screening televisit will be scheduled; Televisit 1b should occur tentatively no later than a week prior to participant taking first dose of study medication. If participants prefer, Televisit #1a and #1b can be combined and completed in a single visit ([Table 1](#)).

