## 6.2 Treatment Period

The first shipment will contain sufficient medication for the first 4 weeks of the study, after which, two more shipments will be triggered for ongoing treatment based on participant response and PI or designee's prescription.

Once study medication is received, the participant will confirm receipt and administration of the first dose within the study mobile app. At all other timepoints, dosing information will be captured during the televisit.

A televisit will be scheduled 4 weeks (28 days), 9 weeks (63 days ) and 14 weeks (98 days) after date of first dose ([Table 1](#), [Figure 1](#)). Participants will need to continue to take study medication as per the instructions provided by the Investigator during the Treatment Period.

	Protocol 812P413	
	Page 26 of 61	Version 2.0

During the Televisit #2 and #3 (Weeks 4 and 9), the following will be administered, obtained or collected by a qualified/trained rater or assessor (ClinRO efficacy assessments should not be administered if participant is discontinuing and has not taken daily dose of Qelbree for >7 consecutive days prior to the televisit):

- AISRS
- CGI-S
- CGI-C
- C-SSRS '*Since Last Visit*' Version
- Review AEs
- Review Concomitant Medications
- Report systolic/diastolic blood pressure, pulse rate, and weight
- Report UPT results (FOCPs only)
- RMCH Questionnaire's Menstrual-Question #5 (FOCPs only)
- SM accountability; Report the number of remaining capsules in bottle
- Confirm or reschedule next virtual visit (Week 9 and Week 14, as applicable)

In addition, at Weeks 4 and 9, the participant will complete the following via the study mobile app (PRO efficacy assessments should not be administered if participant is discontinuing and has not taken daily dose of Qelbree for >7 consecutive days prior to attempting them):

- SM administration mode/time query; report admin method and average admin time
- ASRSv1.1-SC
- PHQ-8
- GAD-7
- WPAI:SHP

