**Table 1. Schedule of Events**

Study Period	Screening Period			Treatment Period			EOS 	SF
Week of Study	–	–	–	–	4	9	14	15
Televisit  No.	1a	1b	–	–	2	3	4	5
Day of Study	- 28 to -1		- 7 to -1	1	29	64	99	106
Window (days)	–	–	–	–	± 3	± 3	± 3	± 3
Informed Consent	X							
Schedule Next Televisit	X	X			X	X	X	
Review Inclusion/Exclusion Criteria	X	X						
Demographics	X							
Medical/Psychiatric/Social History	X							
RMCH Questionnaire	X 	X 			X 	X 	X 	
Review Prior Medications 	X							
Review Concomitant Medications	X	X			X	X	X	X
Review Adverse Events					X	X	X	X
Ship BP/PR cuff 	X							
Ship UPT (FOCP only) 	X							
Confirm Negative UPT (FOCP only)	X				X	X	X	
BP/PR and Weight 	X				X	X	X	
Height 	X							
MINI-AS (DSM-5-TR)	X							
AISRS ( ClinRO )		X			X	X	X	
CGI-S ( ClinRO )		X			X	X	X	
CGI-C ( ClinRO )					X	X	X	
SIGMA ( ClinRO )		X					X	
SIGH-A ( ClinRO )		X					X	
C-SSRS (Baseline/Screening version)	X							
C-SSRS (Since Last Visit version)		X			X	X	X	
Mobile App Training Module (PROs)		X						
Dispense SM			X		X	X		
First Dose of Qelbree 				X				
ASRSv1.1-SC (PRO) 		X			X	X	X	
PHQ-8 (PRO) 		X			X	X	X	

	Protocol 812P413	
	Page 29 of 61	Version 2.0

Study Period	Screening Period			Treatment Period			EOS 	SF
Week of Study	–	–	–	–	4	9	14	15
Televisit  No.	1a	1b	–	–	2	3	4	5
Day of Study	- 28 to -1		- 7 to -1	1	29	64	99	106
Window (days)	–	–	–	–	± 3	± 3	± 3	± 3
GAD-7 (PRO) 		X			X	X	X	
WPAI:SHP (PRO) 		X			X	X	X	
PSQI (PRO) 		X					X	
BRIEF-A (PRO) 		X					X	
SM Administration Mode/Time 					X	X	X	
SM Accountability					X	X	X	
Participant Ship/Return Unused SM 							X	

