5.2. Baseline Definitions

Baseline is defined as the last non-missing assessment measured prior to the start of SM.

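### The Week 4 C-SSRS interval starts before the first dose, and SAP 8.3 does not separate pre-dose from on-treatment answers

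*SAP*

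**What the plan says.** **Analysis.** SAP 8.3 tabulates subjects with a yes "by categories for suicidal ideation, suicidal behavior and suicidal ideation or behavior will be summarized descriptively by visit" and adds a listing. It has no onset date, no split at first dose, no comparison with screening and no definition of treatment-emergent suicidality.

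**Schedule.** Protocol 6.1.1 gives the Baseline/Screening form at Televisit 1a. The Table 1 row that begins "C-SSRS (Since Last Visit version" is marked at 1b, Week 4, Week 9 and Week 14. Nothing is marked on Day 1; under Protocol 6.2 the participant confirms the first dose in the app.

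**Timing of 1b.** Protocol 6.1 says "Televisit 1b should occur tentatively no later than a week prior to participant taking first dose of study medication". Table 1 places both screening televisits anywhere from Day -28 to Day -1. The upper limit comes from 6.1: "The duration of the screening period is up to 4 weeks (28 days) starting from the date of Screening televisit". The same section adds: "If participants prefer, Televisit #1a and #1b can be combined and completed in a single visit".

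**Form used at 1b.** Protocol 6.1.2 and Table 1 use the Since Last Visit form. Protocol 9.4.3 assigns the Baseline/Screening form to screening and the Since Last Visit form to treatment.

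**Related rules.** SAP 5.7 analyzes by nominal visit and maps an early-termination visit to the next scheduled one. SAP 5.2 has a general rule: "Baseline is defined as the last non-missing assessment measured prior to the start of SM".

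**The concern.** Suicidality is a named safety endpoint, and suicidal thoughts and behavior are the first event of concern in Protocol 3.3.1, which reports that among 189 adults on Qelbree "a total of three participants (1.6%) reported suicidal ideation on the C-SSRS, versus 0 of 183 adults treated with placebo". Participants here enter with MADRS and/or HAM-A above 22. Exclusion criterion 6 removes, by score, only ideation items 4 or 5 or suicidal behavior in the previous 6 months, so lower-level ideation can be present before drug. There is no control arm, and timing relative to first dose is therefore a main basis for interpreting a positive answer.

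The other safety endpoints have that separation. AE collection starts at first dose and earlier health changes go to medical history (Protocol 9.5.3). SAP 8.1 defines treatment-emergent events from first dose. SAP 8.2 gives vital signs a change from baseline and shift tables. The C-SSRS table has nothing comparable.

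The error can run either way. Pre-drug ideation can inflate an apparent drug signal at Week 4, or a real early signal can be dismissed as pre-existing because the table cannot show otherwise.

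**Working it through.** **1. Reproduce the visit day.** Protocol 6.2: "A televisit will be scheduled 4 weeks (28 days), 9 weeks (63 days ) and 14 weeks (98 days) after date of first dose". With first dose on Day 1, Week 4 is 1 + 28 = Day 29, as in Table 1. The window of 3 days either side gives 25 to 31 days after first dose.

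**2. Find the start of the Week 4 interval.** The C-SSRS sequence is 1a, 1b, Week 4, Week 9, Week 14. The visit before Week 4 is 1b, so the Week 4 form covers 1b to Week 4 and includes all the days between 1b and first dose. This holds whichever form is used at 1b.

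**3. Pre-drug share.** Let L be the days from 1b to first dose and T the days from first dose to the visit. The share is L/(L+T). L runs from 1 (Table 1) to 28 (6.1 and Table 1), and is at least 7 if the tentative rule in 6.1 is kept.

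| L (days) | Share at T = 28 | Share over T = 31 to 25 |
|---|---|---|
| 1 | 1/29 = 3.4% | 3.1% to 3.8% |
| 7 | 7/35 = 20.0% | 18.4% to 21.9% |
| 14 | 14/42 = 33.3% | 31.1% to 35.9% |
| 21 | 21/49 = 42.9% | 40.4% to 45.7% |
| 28 | 28/56 = 50.0% | 47.5% to 52.8% |

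L = 28 requires 1a and 1b on the same day at the very start of screening, because the 28 days run from 1a.

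**4. Early termination.** Protocol 6.3 asks for the Week 14 assessments at early termination; the restriction after more than 7 days off drug applies to efficacy scales only, so the C-SSRS is still due. SAP 5.7 reports a termination before Week 4 as Week 4. With T = 7:
- L = 1: 1/8 = 12.5%
- L = 7: 7/14 = 50%
- L = 28: 28/35 = 80%

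**5. Later visits.** If Week 4 was done, the Week 9 interval starts on treatment, and likewise Week 14 after Week 9. If Week 4 was missed, Week 9 reaches back to 1b: with L = 7, 7/(7+63) = 10%.

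**6. What SAP 8.3 does with these answers.** A participant with ideation only between 1b and first dose answers yes at Week 4 and is counted in the Week 4 row. No rule removes or marks that answer.

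**The case against.** The strongest reply is that this is a descriptive study without hypotheses (SAP 5.5), that SAP 8.3 labels rows by visit and never calls them treatment-emergent, and that suicidal events can also be reported as AEs, which carry start dates and are collected only after first dose. All of this is true. The AE route is a partial, dated source. It does not replace the split on the C-SSRS, the instrument named for the endpoint. The Week 4 row sits in the treatment period, and the SAP gives the reader no means of reading it otherwise. The listing helps only if onset relative to first dose is collected, and the documents do not say that it is.

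It can also be said that the gap may be short. That stands as to range: a gap of 1 day gives only 3.4%. Protocol 6.1.2 has the medication shipped after 1b, however, so so short a gap looks unlikely, and any gap of a day or more brings pre-dose time in.

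A reader might infer more than the documents support:
- *That the baseline rule in SAP 5.2 causes the problem.* SAP 8.3 makes no comparison with a C-SSRS baseline, so the rule does not enter that table. The 1a form is collected and can be shown.
- *That a combined screening visit leaves an empty baseline interval.* The documents do not say that both forms are given at a combined visit, and 9.4.3 points to the Baseline/Screening form alone.
- *That ideation months before screening reappears at Week 4.* It cannot by itself, because the Week 4 form asks only about the time since 1b.
- *That 3% to 50% of Week 4 positives are pre-drug.* A share of days equals a share of positives only for rare, isolated events at a constant rate. Persistent ideation would be a yes either way. The documents give no ideation rate for this population, so no count of misattributed participants can be derived.

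**Conclusion.** The point holds for Week 4 and for early terminations mapped to it. If the plan is followed exactly, the Week 4 C-SSRS row mixes pre-drug and on-drug time, and ideation that occurred only before drug can be read as occurring on treatment. The pre-drug part of the scheduled recall is about 3% to 50%, and 20% with 1b at 7 days. It reaches 80% for a termination 7 days after first dose when 1b was 28 days before it.

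These figures rest on the Table 1 limits for 1b and on Week 4 at 28 days after first dose; the window of 3 days either side moves them to between 3.1% and 52.8%. Misattribution of a given answer is possible, not certain. Weeks 9 and 14 are unaffected when the preceding C-SSRS was done. The primary endpoint is not touched. The change is worth making because it bears on a named safety endpoint in an uncontrolled trial and costs little.

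**What to change.** 1. **Data.** At the first C-SSRS after dosing (Week 4, or an early-termination visit mapped to it; Week 9 if Week 4 was missed), record for each positive category whether it occurred before first dose, on or after first dose, or both. The first-dose date is already captured in the app (Table 1, footnote 8).
2. **SAP 8.3.** Count as on-treatment only answers that occurred on or after first dose, including those marked both. Count undatable answers as on-treatment. Show pre-dose answers separately, with the 1a and 1b screening results.
3. **Reconcile the protocol.** Protocol 6.1 and Table 1 differ on how close to first dose 1b may fall. Protocol 6.1.2 and Table 1 differ from 9.4.3 on the C-SSRS form at 1b. State also which form or forms apply when 1a and 1b are combined.

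**Cost.** A small eCRF addition, in effect at one visit per participant, and a paragraph in SAP 8.3. No new visit is needed. Dating by recall will bring some error; counting undatable answers as on-treatment keeps them from being dropped from the on-treatment count.

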## 7.2 Exclusion Criteria

A participant who meets any of the following criteria will be excluded from participation in the study:

1. Has a history of substance use disorder (alcohol, opioids, etc.) within the last 6 months prior to providing informed consent with exception of nicotine and cannabis.
2. Is currently taking or has taken Qelbree for treatment of ADHD in the last 3 months or is currently taking another non-stimulant medication for treatment of ADHD, like atomoxetine (Strattera), Clonidine (Catapres, Kapvay) or Guanfacine (Tenex, Intuniv). Stimulant medications for ADHD and most medications for mood symptoms (symptoms of depression and/or anxiety) are allowed.
3. Is taking a prohibited concomitant medication per the Qelbree Prescribing Information.
4. Is a FOCP who is pregnant, nursing, sexually active with a male partner and not willing to use one of the acceptable birth control methods throughout the study and/or is seeking fertility treatment.
5. Has history of moderate or severe head trauma or other neurological disorder or systemic medical disease that, in the Investigator's opinion, is likely to affect central nervous system functioning. This would include participants with:
  - a) A current diagnosis of a major neurological disorder; or
  - b) Seizures, seizure disorder or seizure-like events; or a history of seizure disorder within the immediate family (siblings, parents); or
  - c) Encephalopathy
6. Has attempted suicide within the 6 months prior to the C-SSRS assessment at Screening, or is at significant risk of suicide, either in the opinion of the Investigator or defined as a "yes" to suicidal ideation questions 4 or 5 or answering "yes" to suicidal behavior on the C-SSRS within the 6 months prior to the C-SSRS assessment at Screening.
7. Is currently participating in another clinical trial or has participated in a clinical trial within the 60 days prior to providing informed consent.
8. Has any history of schizophrenia, schizoaffective disorder, or bipolar disorder, or has any other psychiatric disorders in the Investigator's clinical judgement would interfere with their ability to participate in the study.
9. Has any unstable, clinically significant cardiovascular condition that in the Investigator's clinical judgement would preclude their participating in the study.

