## 12.9 Safety Analysis

Safety analyses will be performed based on the safety analysis set.

[figure not shown]
AEs will be classified into standardized medical terminology from the Verbatim description (Investigator term) using the Medical Dictionary for Regulatory Activities (MedDRA) and Preferred Term (PT).

The incidence rate, severity, and relationship to Qelbree for all AEs will be summarized for each System Organ Class (SOC) and PT. The absolute and change from baseline for blood pressure, pulse rate, and weight will be presented will be summarized using descriptive statistics by study visit.

Columbia Suicide Severity Rating Scale (C-SSRS) outcomes will be summarized using number and percent of participants by categories for suicidal ideation, suicidal behavior and suicidal ideation or behavior.

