8.2.2. Shift in Vital Signs

Compared to the reference range, each of the three vital signs variables (diastolic blood pressure, systolic blood pressure and pulse rate) values will be classified as low, normal, high or missing. Shift tables for the change from baseline to all study visits will be summarized using number and percentage of subjects by visit.

Vital sign normal ranges are presented in [Table 1](#).

Table 1. Vital Signs Normal Ranges

Parameter	Low	High
Diastolic blood pressure (mmHg)	60	90
Systolic blood pressure (mmHg)	90	140
Pulse rate	50	100

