11. APPENDICES

Table 2. Schedule of Procedures and Assessments

Study Period	Screening Period			Treatment Period			EOS ¹⁰	SF
Week of Study	—	—	—	—	4	9	14	15
Televisit ¹ No.	1a	1b	—	—	2	3	4	5
Day of Study	- 28 to -1		- 7 to -1	1	29	64	99	106
Window (days)	—	—	—	—	± 3	± 3	± 3	± 3
Informed Consent	X							
Schedule Next Televisit	X	X			X	X	X	
Review Inclusion/Exclusion Criteria	X	X						
Demographics	X							
Medical/Psychiatric/Social History	X							
RMCH Questionnaire	X ²	X ²			X ³	X ³	X ³	
Review Prior Medications ⁴	X							
Review Concomitant Medications	X	X			X	X	X	X
Review Adverse Events					X	X	X	X
Ship BP/PR cuff ⁵	X							
Ship UPT (FOCP only) ⁵	X							
Confirm Negative UPT (FOCP only)	X				X	X	X	
BP/PR and Weight ^{5,6}	X				X	X	X	
Height ⁷	X							
MINI-AS (DSM-5-TR)	X							
AISRS (ClinRO)		X			X	X	X	
CGI-S (ClinRO)		X			X	X	X	
CGI-C (ClinRO)					X	X	X	
SIGMA (ClinRO)		X					X	
SIGH-A (ClinRO)		X					X	
C-SSRS (Baseline/Screening version)	X							
C-SSRS (Since Last Visit version)		X			X	X	X	
Mobile App Training Module (PROs)		X						
Dispense SM			X		X	X		
First Dose of Qelbree ⁸				X				
ASRSv1.1-SC (PRO) ⁹		X			X	X	X	
PHQ-8 (PRO) ⁹		X			X	X	X	

Study Period	Screening Period			Treatment Period			EOS ¹⁰	SF
Week of Study	—	—	—	—	4	9	14	15
Televisit ¹ No.	1a	1b	—	—	2	3	4	5
Day of Study	- 28 to -1		- 7 to -1	1	29	64	99	106
Window (days)	—	—	—	—	± 3	± 3	± 3	± 3
GAD-7 (PRO) ⁹		X			X	X	X	
WPAI:SHP (PRO) ⁹		X			X	X	X	
PSQI (PRO) ⁹		X					X	
BRIEF-A (PRO) ⁹		X					X	
SM Administration Mode/Time ⁹					X	X	X	
SM Accountability					X	X	X	
Participant Ship/Return Unused SM ¹⁰							X	

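### The planned C-SSRS tables cannot separate new or worsened suicidal ideation on Qelbree from level 1-3 ideation that was present before dosing and persists.

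*SAP*

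**What the plan says.** - **SAP 8.3** is the whole C-SSRS analysis: the number and percentage of subjects with a Yes, "by categories for suicidal ideation, suicidal behavior and suicidal ideation or behavior will be summarized descriptively by visit". It then adds: "The listing for C-SSRS will be provided".
- **Protocol 12.9** plans no more: C-SSRS "outcomes will be summarized using number and percent of participants by categories for suicidal ideation, suicidal behavior and suicidal ideation or behavior". Neither document defines new or worsened ideation or behavior.
- **Other safety endpoints are compared with pre-dose status.** For blood pressure and pulse, SAP 8.2.2 states: "Shift tables for the change from baseline to all study visits will be summarized using number and percentage of subjects by visit". SAP 8.1 defines treatment-emergent adverse events so as to include worsening after the first dose.
- **Entry.** Protocol 7.2, criterion 6, excludes a Yes to "suicidal ideation questions 4 or 5" or to suicidal behavior in the six months before screening, and anyone the Investigator judges at significant risk. It does not otherwise exclude levels 1-3. Protocol 7.1, criterion 6, requires a MADRS and/or HAM-A total above 22.
- **Forms.** In the schedule (Protocol Table 1, SAP Table 2) the Baseline/Screening form is used at Televisit 1a only. The Since Last Visit form is used at Televisit 1b and at Weeks 4, 9 and 14.
- **General rules.** SAP 5.2 takes the last non-missing pre-dose assessment as baseline. SAP 5.1 leaves unscheduled measurements out of by-visit tables. Protocol 6.1 lets Televisits 1a and 1b be held as one visit.

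**The concern.** Suicidal thoughts and behavior come first among the adverse events of concern in Protocol 3.3.1. The safety question is whether ideation starts or gets worse after dosing, which is a question about change within a person. A table of Yes counts at each visit answers a different one: how many people report ideation in that interval. Someone whose level 1 ideation is unchanged since before dosing adds to the on-treatment count exactly as a new case does.

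This matters more here than in the earlier adult placebo-controlled trial (Study 812P306), because Protocol 3.1 says that the earlier trials excluded depression and anxiety. A high on-treatment percentage in this study could be read as a drug signal when most of it was carried in. A flat percentage could be read as reassurance when new cases have replaced resolved ones.

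**Working it through.** **1. The plan's own figures.** Protocol 3.3.1 reports for the earlier trial that "a total of three participants (1.6%) reported suicidal ideation on the C-SSRS", out of 189 treated with Qelbree, against 0 of 183 on placebo. 3/189 = 1.59%, which rounds to 1.6% and reproduces. It is the only C-SSRS rate in the documents. Protocol 12.3 gives up to 750 dosed, 33% attrition and up to 500 completers: 750 × (1 − 0.33) = 502.5, which agrees with 500.

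**2. What two visit counts say about new cases.** Take the same N people, with y0 Yes before dosing and y1 Yes at a later visit. The number who were No and became Yes lies between max(0, y1 − y0) and min(y1, N − y0). With N = 500 and equal counts at both times:

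| Yes at each time | New cases compatible with the table |
|---|---|
| 25 (5%) | 0 to 25 |
| 50 (10%) | 0 to 50 |
| 100 (20%) | 0 to 100 |
| 150 (30%) | 0 to 150 |

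The percentages are examples, but the width of the range follows from the form of the table. In practice the same people are not present at both times, since up to 750 start and up to 500 finish. The real comparison is looser still.

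**3. Does showing individual levels cure this?** No. Split the 100 Yes into 50 at level 1 and 50 at level 3, before and after. The same rows arise if nobody moves, or if all 50 at level 1 rise to level 3 while all 50 at level 3 fall to level 1. Worsening among those 100 people could be anywhere from 0 to 50.

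**4. Illustration of size (assumed inputs).** Let b be the share with level 1-3 ideation before dosing, s the share of those who still report it on drug, and 3/189 the onset rate among the rest. The documents give neither b nor s; I take b = 5-30% and s = 50-100%. They also do not say that 3/189 was new onset, so using it that way is a further assumption.

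On-treatment Yes rate = b × s + (1 − b) × 3/189.

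- Low end: 0.05 × 0.5 + 0.95 × 0.0159 = 0.025 + 0.0151 = 4.0%. Carried over: 0.025/0.0401 = 62%. New cases per 750: 750 × 0.0151 = 11.3.
- High end: 0.30 × 1.0 + 0.70 × 0.0159 = 0.300 + 0.0111 = 31.1%. Carried over: 0.300/0.3111 = 96%. New cases per 750: 750 × 0.0111 = 8.3.

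Under these assumptions the number of new cases hardly moves (about 8 to 11 per 750) while the tabulated percentage runs from 4.0% to 31.1%.

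**5. Which baseline a shift table would use.** Under SAP 5.2 the C-SSRS baseline is the Televisit 1b form, which asks only about the time since 1a. If 1a and 1b are combined, that interval is about zero. Ideation reported at 1a could then be a No at baseline, and its persistence on drug would be classed as new. A shift table built on the general rule would inherit this problem.

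**The case against.** Several counter-arguments are fair, and they limit what can be claimed.

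- **Worsening is not invisible.** A reader might infer that it cannot be seen at all. The documents do not support that. The listing holds each subject's answers before and after dosing. Adverse events are asked about at every contact (Protocol 9.4.1), and worsening counts as treatment-emergent (SAP 8.1). Any post-dose level 4-5 ideation or suicidal behavior in a correctly enrolled subject is new against the six-month look-back. This stands. But the listing could run to 750 × 5 = 3,750 scheduled forms with no rule for what is new, and nothing requires a C-SSRS change to be entered as an adverse event.
- **Past history alone does not count on drug.** A reader might infer that lifetime ideation inflates the table. Post-dose visits use the Since Last Visit form, so only ideation reported for that interval is counted. The problem is persisting ideation.
- **The categories may be individual levels.** Protocol 9.4.3 describes 11 C-SSRS categories, and SAP 8.3 does not say which rows it means. If levels are shown, level 4-5 entries would stand out and a move from level 1 to level 3 would alter the rows. The rows still could not be linked to a person (step 3).
- **Screening may appear in the by-visit table.** SAP 8.3 does not say. If it does, pre-dose prevalence is visible, but only for the group and with a changing denominator.
- **The study is single-arm and descriptive**, with no formal hypotheses (SAP 5.5). A shift table cannot tell a drug effect from natural fluctuation. True, but it would at least describe change, which the planned table does not.

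**Conclusion.** The point holds for the summary tables. As planned, they cannot separate new or worsened ideation from level 1-3 ideation that was present before dosing and persists. Equal counts of 100 in 500 fit 0 to 100 new cases, and that rests on arithmetic alone. It also needs some level 1-3 ideation at entry, which the eligibility criteria allow but the documents do not quantify.

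The figures of 4.0-31.1% on-treatment Yes and 62-96% carried over are illustration only. A reader might set such percentages against the earlier 1.6% and infer a several-fold distortion. The documents do not support this: they give no prevalence or persistence, and they do not say whether the 1.6% was new onset, at any visit or by visit.

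This is a reporting gap on a leading safety concern that is cheap to close. It does not touch the efficacy analyses or the collection of C-SSRS data.

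**What to change.** In SAP 8.3, add:

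1. A shift table from the highest pre-dose C-SSRS category to the highest post-dose category at any time. It should include unscheduled assessments, which SAP 5.1 drops only from by-visit summaries.
2. The number and percentage with new ideation or behavior (none pre-dose, any post-dose), and with worsened ideation (a higher level post-dose than pre-dose).
3. A C-SSRS baseline separate from SAP 5.2: the worst response over Televisits 1a and 1b, for a stated recall period that the form actually records. Where the 1a form records both recent and longer recall, show both. A long look-back alone would hide recurrence: someone at level 3 five months ago, at none before dosing and at level 3 on drug would appear unchanged. The six-month window in the exclusion criterion should not simply be borrowed, because no section says that levels 1-3 are recorded over it.
4. A statement of whether the rows in the by-visit table are individual levels, and whether screening is shown.

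The cost is one extra table, built from C-SSRS forms already scheduled. The limitation is that pre-dose and post-dose recall windows differ in length, which a footnote should state.
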